### 5.2.6 Assessment of adverse events

#### 5.2.6.1 Definitions of AEs

##### 5.2.6.1.1 Adverse event

An AE is defined as any untoward medical occurrence in a patient or clinical investigation subject administered a medicinal product and which does not necessarily have to have a causal relationship with this treatment.

An AE can therefore be any unfavourable and unintended sign (including an abnormal laboratory finding), symptom, or disease temporally associated with the use of a medicinal product, whether or not considered related to the medicinal product.

The following should also be recorded as an AE in the CRF and BI SAE form (if applicable):

- Worsening of the underlying disease or of other pre-existing conditions
- Changes in vital signs, ECG, physical examination and laboratory test results, if they are judged clinically relevant by the investigator.

If such abnormalities already exist prior to trial inclusion, they will be considered as baseline conditions and should be collected in the eCRF only.

### 5.2.6.1.2 Serious adverse event

A serious adverse event (SAE) is defined as any AE, which fulfils at least one of the following criteria:

- results in death,
- is life-threatening, which refers to an event in which the patient was at risk of death at the time of the event; it does not refer to an event that hypothetically might have caused death if more severe,
- requires inpatient hospitalisation or prolongation of existing hospitalisation
- results in persistent or significant disability or incapacity,
- is a congenital anomaly / birth defect,
- is deemed serious for any other reason if it is an important medical event when based on appropriate medical judgement which may jeopardise the patient and may require medical or surgical intervention to prevent one of the other outcomes listed in the above definitions. Examples of such events are intensive treatment in an emergency room or at home for allergic bronchospasm, blood dyscrasias or convulsions that do not result in hospitalisation or development of dependency or abuse.

For Japan only: the following events will be handled as “deemed serious for any other reason”. AEs which possibly lead to disability will be reported as SAEs.

### 5.2.6.1.3 AEs considered “Always Serious”

In accordance with the European Medicines Agency initiative on Important Medical Events, Boehringer Ingelheim has set up a list of AEs, which by their nature, can always be considered to be “serious” even though they may not have met the criteria of an SAE as defined above.

The latest list of “Always Serious AEs” can be found in the EDC system. A copy of the latest list of “Always Serious AEs” will be provided upon request. These events should always be reported as SAEs as described in [section 5.2.6.2](#).

Cancers of new histology and exacerbations of existing cancer must be classified as a serious event regardless of the time since discontinuation of the drug and must be reported as described in Section 5.2.6.2, subsections “AE Collection” and “AE reporting to sponsor and timelines”.

### 5.2.6.1.4 Suicidal Risk assessed by the C-SSRS

All reports of suicidal behaviour and all C-SSRS reports of suicidal ideation type 4 or 5 must be reported as SAEs by the investigator.

For each instance of suicidal ideation type 1, 2 or 3 after start of the trial, the investigator is to decide based on clinical judgement whether it represents an AE as defined in the protocol. If this

is considered as AE, then it must be reported as SAE, using SAE form and eCRF AE page, as this is listed on the “BI always serious adverse event list”.

For ‘Self-injurious behaviour, no suicidal intent’ standard AE/SAE reporting rules are to be applied.

#### **5.2.6.1.5 Adverse events of special interest**

The term adverse events of special interest (AESI) relates to any specific AE that has been identified at the project level as being of particular concern for prospective safety monitoring and safety assessment within this trial, e.g. the potential for AEs based on knowledge from other compounds in the same class. AESIs need to be reported to the sponsor’s Pharmacovigilance Department within the same timeframe that applies to SAEs, please see [section 5.2.6.2.2](#).

The following are considered as AESIs:

##### Hepatic injury

A hepatic injury is defined by the following alterations of hepatic laboratory parameters:

- an elevation of AST (Aspartate Aminotransferase) and/or ALT (Alanine Aminotransferase)  $\geq 3$  fold ULN combined with an elevation of total bilirubin  $\geq 2$  fold ULN measured in the same blood draw sample, or
- aminotransferase (ALT, and/or AST) elevations  $\geq 10$  fold ULN.

These lab findings constitute a hepatic injury alert and the patients showing these lab abnormalities need to be followed up according to the “DILI checklist”.

In case of clinical symptoms of hepatic injury (icterus, unexplained encephalopathy, unexplained coagulopathy, right upper quadrant abdominal pain, etc.) without lab results (ALT, AST, total bilirubin) available, the investigator should make sure these parameters are analysed, if necessary in an unscheduled blood test. Should the results meet the criteria of hepatic injury alert, the procedures described in the DILI checklist should be followed.

#### **5.2.6.1.6 Intensity (severity) of AEs**

The intensity (severity) of the AE should be judged based on the following:

Mild: Awareness of sign(s) or symptom(s) that is/are easily tolerated.  
Moderate: Sufficient discomfort to cause interference with usual activity.  
Severe: Incapacitating or causing inability to work or to perform usual activities.

#### **5.2.6.1.7 Causal relationship of AEs**

Medical judgement should be used to determine whether there is a reasonable possibility of a causal relationship between the adverse event and the given study treatment, considering all relevant factors, including pattern of reaction, temporal relationship, de-challenge or re-

challenge, confounding factors such as concomitant medication, concomitant diseases and relevant history.

Arguments that may suggest that there is a reasonable possibility of a causal relationship could be:

- The event is consistent with the known pharmacology of the drug.
- The event is known to be caused by or attributed to the drug class.
- A plausible time to onset of the event relative to the time of drug exposure.
- Evidence that the event is reproducible when the drug is re-introduced.
- No medically sound alternative aetiologies that could explain the event (e.g. pre-existing or concomitant diseases, or co-medications).
- The event is typically drug-related and infrequent in the general population not exposed to drugs (e.g. Stevens-Johnson syndrome).
- An indication of dose-response (i.e. greater effect size if the dose is increased, smaller effect size if dose is reduced).

Arguments that may suggest that there is no reasonable possibility of a causal relationship could be:

- No plausible time to onset of the event relative to the time of drug exposure is evident (e.g. pre-treatment cases, diagnosis of cancer or chronic disease within days / weeks of drug administration; an allergic reaction weeks after discontinuation of the drug concerned).
- Continuation of the event despite the withdrawal of the medication, taking into account the pharmacological properties of the compound (e.g. after 5 half-lives).  
Of note, this criterion may not be applicable to events whose time course is prolonged despite removing the original trigger.
- Additional arguments amongst those stated before, like alternative explanation (e.g. situations where other drugs or underlying diseases appear to provide a more likely explanation for the observed event than the drug concerned).
- Disappearance of the event even though the trial drug treatment continues or remains unchanged.

### 5.2.6.2 Adverse event collection and reporting

#### 5.2.6.2.1 AE Collection

The investigator shall maintain and keep detailed records of all AEs in the patient files.

The following must be collected and documented on the appropriate CRF(s) by the investigator:

- **For patients who roll-over to the extension trial:**
  - From signing informed consent onwards until first dose of trial medication in the extension trial: all AEs (serious and non-serious) and all AESIs. Updates to

concomitant therapy should also be included until first dose of trial medication in the extension trial.

**Note:** Updates for SAEs and/ or AESIs ongoing at the time of rollover to the extension trial, must be also updated in parent trial, in addition to the extension trial, as long as the data base of parent trial is not locked. On SAE form, updates for events reportable on SAE form with onset in parent trial are only reported into the parent trial.

- **For patients who do not roll-over to the extension trial:**
  - From signing the informed consent onwards until the 28 days (F2 visit) after the end of treatment visit: all AEs (serious and non-serious) and all AESIs.
  - **After the individual patient's end of trial:** The investigator does not need to actively monitor the patient for new AEs but should only report any occurrence of cancer and trial treatment related SAEs and trial treatment related AESIs of which the investigator may become aware of by any means of communication, e.g. phone call. Those AEs should be reported on the BI SAE form (see section 5.2.6.2.2), but not on the CRF.
- **For patients who permanently discontinue trial medication prematurely:**
  - From signing the informed consent onwards until the 28 days (Follow-up 2 visit) after the early end of treatment visit: all AEs (serious and non-serious) and all AESIs.
  - **From Follow-up 2 visit up to the individual patients' planned end of Trial (i.e. 26 weeks/visit 11):** Until the individual patient's planned end of trial, the investigator must report
    - Treatment related SAEs / AESIs
    - Following regardless of causal relationship
      - Anaemia
      - SAEs from C-SSRS assessments
      - Any occurrence of cancer
      - Deaths/ fatal AEs
  - **After the individual patient's planned end of trial (i.e. 26 weeks/ completion of visit 11):** The investigator does not need to actively monitor the patient for new AEs but should only report any occurrence of cancer and trial treatment related SAEs and trial treatment related AESIs of which the investigator may become aware of by any means of communication, e.g. phone call. Those AEs should be reported on the BI SAE form (see section 5.2.6.2.2), but not on the CRF.

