#### **2.2.2.2      Further safety endpoints**

- Disease under study monitored using:
- PANSS total score and change from baseline
- Incidence of relapse
- SAS/BARS/AIMS Scale scores throughout the treatment
- Suicidality as assessed by C-SSRS
- Occurrence of protocol specified AESI
- Percentage of patients with (S)AEs (including clinically relevant abnormalities of physical examination, vital signs, ECG test and laboratory tests)

[REDACTED]

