### 5.2.5 Other safety parameters

Assessment of disease state:

PANSS will be used to evaluate the disease severity. Refer to [Section 5.2](#). In addition investigator may use CGI-S and his/her clinical judgment for assessing schizophrenia worsening/relapse.

**Schizophrenia worsening (i.e., deterioration of chronic residual symptoms):** Fluctuation in the severity of symptoms is common and should be managed and reported as per the clinical judgment of the investigator. Adjustment of background medication is allowed when necessary. In such cases, schizophrenia worsening must be reported as adverse event per the clinical judgment of the investigator.

**Schizophrenia Relapse (acute episode):** If **severity** of schizophrenia symptoms fulfills the criteria of relapse (acute episode), investigator must report relapse as adverse event. Definition of relapse for this program is: Increased level of care (such as hospitalization, home hospitalization, emergency room (ER) visit due to psychotic symptoms) due to worsening of psychotic symptoms / increased PANSS per investigators judgment.

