| Scenario #4
(assumed standardized effect sizes) | 0.35                  | 0.1                              | 0.25                  | 0.2                        | 0.275             |  |
| Probability of rejecting null from 1000000 simulations    | 95.6%                 | 12.5%                            | 62.7%                 | 30.0%                      | 46.7%             | 65.2%  |
| Scenario #5
(assumed standardized effect sizes) | 0.35                  | 0                                | 0                     | 0.2                        | 0.275             |  |
| Probability of rejecting null from 1000000 simulations    | 95.6%                 | 1.3%                             | 1.3%                  | 1.5%                       | 2.0%              | 2.4%   |

With 220 evaluable subjects per arm, one-sided family-wise type I error rate =0.025, correlation between the endpoints = 0.2, truncation parameter  $\gamma = 0.2$ , and the gatekeeping procedure as shown in [Figure 7.1: 1](#).

Based on the proportions of early treatment termination, subjects with missing data and missing data patterns as observed in our phase II trial 1346-0009 and anticipating higher proportions of early treatment termination based on previous literatures in long-term antipsychotic trials and more subjects with missing data in our phase III trial due to longer treatment duration, we project 30% to 40% subjects will prematurely terminate treatment in our phase III trial. Since BI will take every measure to collect all data at the planned visits from early dropout subjects, we anticipate 25% to 50% of these early dropouts will have efficacy outcomes collected after treatment termination and can be used in the analysis. Based on these estimations, we will apply

Proprietary confidential information © 2024 Boehringer Ingelheim International GmbH or one or more of its affiliated companies

25% correction for missing data in the sample size calculation for this phase III trial. This gives a total number of 586 randomized subjects for the phase III trial, with 293 randomized subjects in each treatment arm.

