An overall summary of adverse events will be presented, including frequency of schizophrenia relapse. The frequency of subjects with AEs will be summarised by treatment, primary system organ class (SOC) and preferred term (PT). The SOCs will be sorted by default in descending frequency and PTs will be sorted in descending frequency within an SOC in the iclepirtin arm. Separate tables will be provided for patients with

- Related AEs
- Serious AEs
- Serious related AEs
- AESIs
- Other significant AEs
- AEs leading to death
- AE leading to discontinuation of trial medication
- AEs occurred with incidence in the preferred term >2%
- AEs suggestive of abuse potential or related to CNS depressant effects
- AEs in user-defined AE categories
- AEs occurred during the follow-up period.

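### For early stoppers, a relapse that is non-serious or judged unrelated need not be reported as an AE between Follow-up 2 and Week 26, although relapse incidence is a stated safety endpoint

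*Protocol*

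**What the plan says.** Protocol Section 2.2.2.2 lists "Incidence of relapse" among the further safety endpoints and gives no observation window. Section 5.2.5 defines relapse as "Increased level of care (such as hospitalization, home hospitalization, emergency room (ER) visit due to psychotic symptoms") that follows from worsening psychotic symptoms or a raised PANSS, in the investigator's judgement. It then says the "investigator must report relapse as adverse event", again without a time limit.

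Section 5.2.6.2.1 sets two periods for patients who stop trial drug permanently before Week 26:

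- **Consent to Follow-up 2.** Collection is complete: "until the 28 days (Follow-up 2 visit) after the early end of treatment visit: all AEs (serious and non-serious) and all AESIs".
- **Follow-up 2 to Week 26.** Up to the patient's "planned end of trial, the investigator must report" a shorter list: "Treatment related SAEs / AESIs" plus four categories reported whatever their cause, namely anaemia, SAEs arising from the C-SSRS, cancer, and deaths.

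Table 6.2.5.1:1 and Section 6.2.5.2 both point back to Section 5.2.6.2.1 for AE collection in these patients. On how many there will be, Section 7.5 says "we project 30% to 40% subjects will prematurely terminate treatment in our phase III trial".

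SAP 7.8.1 bases AE analysis on treatment-emergent events, up to the last dose plus 12 days. It says "An overall summary of adverse events will be presented, including frequency of schizophrenia relapse". It assigns later events to follow-up and plans a separate table of AEs in that period.

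**The concern.** Completers are observed for relapse over the full 26 weeks. A patient who stops at Week 6 has complete relapse reporting for only about five more weeks. After that, a relapse counts as a required AE only if it is both serious and drug-related, or if it also meets one of the listed categories. The first route is narrow. Follow-up 2 comes at least 28 days after the last dose, well past the 12-day residual effect period, and Section 5.2.6.1.7 treats an implausible time to onset as an argument against causality.

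Sites will often know about these events. Section 6.2.1 requires efficacy testing to be postponed while a patient is in relapse, and early stoppers are asked to keep attending. The event would be recognised at the visit and recorded in the patient file without having to be entered as an AE.

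At stake is an endpoint whose follow-up depends on when treatment stopped. The SAP's follow-up-period AE table would hold all relapses of early stoppers up to Follow-up 2 and few after it, purely because of the collection rule. Off-treatment relapse data also bear on the statement in Table 1.4.2:1 that stopping study drug carries no higher risk of relapse.

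**Working it through.** **Inputs from the documents.** 586 randomised; 30% to 40% early stopping (Section 7.5). Early end-of-treatment visit preferably within 7 days of the last dose (6.2.5.1). Follow-up 2 at 28 days after that visit (6.2.5.2), with a window of +7 days (Flow Chart). Week 26 is Day 183, so planned treatment time is 182 days.

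**Assumption.** The documents give no distribution of stopping times. I take them as uniform over 182 days and vary this below.

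**The plan's own figure.** 220 / 0.75 = 293.3, stated as 293 per arm, or 586 in total. Early stoppers: 586 × 0.30 = 176 to 586 × 0.40 = 234.

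**Who is affected.** A gap exists only if stop day + lag falls before Day 183.

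| Lag, last dose to Follow-up 2 | Stops before | Share of stoppers | Patients (30% to 40% stopping) |
|---|---|---|---|
| 28 days | Day 155 (Week 22) | 154/182 = 84.6% | 149 to 198 |
| 35 days | Day 148 (Week 21) | 147/182 = 80.8% | 142 to 189 |
| 42 days | Day 141 (Week 20) | 140/182 = 76.9% | 135 to 180 |

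**Uncovered patient-time.** The mean gap per stopper, as a share of 182 days, is (182 − lag)² / (2 × 182²).

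- Lag 35: 147² / 66,248 = 32.6%. Times 0.30 to 0.40, this is **9.8% to 13.0%** of all planned patient-time.
- Lag 28: 35.8%, giving 10.7% to 14.3%.
- Lag 42: 29.6%, giving 8.9% to 11.8%.

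**Sensitivity to stopping time (lag 35).**

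- All stops in the first half: mean gap 147 − 45.5 = 101.5 days, or 55.8% of 182. Uncovered share 17% to 22%.
- All stops in the second half: mean gap 56² / (2 × 91) = 17.2 days, or 9.5% of 182. Uncovered share 3% to 4%.

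**Share of relapses in the gap (lag 35, uniform stopping, low event rate).** With equal hazard throughout, the share equals the patient-time share, 10% to 13%. If the hazard doubled after stopping, total risk rises as well. Stoppers spend on average half the 182 days off drug, which adds 0.5 × 0.30 = 0.15 to 0.5 × 0.40 = 0.20. The share is then 2 × 0.098 / 1.15 = 17% to 2 × 0.130 / 1.20 = 22%. The doubling is illustrative; the documents give no hazard.

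**Treatment-emergent count.** Its window closes 12 days after the last dose. Follow-up 2 is at least 28 days after it. Since 12 < 28, every treatment-emergent relapse falls within the period of full AE collection.

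**The case against.** The best defence is that the two sections do different jobs. Section 5.2.5 says what a relapse is and that it is an AE; Section 5.2.6.2.1 says when AEs are collected. Taken literally, Section 5.2.5 would also clash with the rule for the time after trial end, so a general duty limited by a specific window is a normal structure. Section 3.2 explains why 28 days is considered enough. This makes the contradiction less stark, but it does not supply a window for the relapse endpoint. The protocol also already keeps anaemia and C-SSRS events reportable whatever their cause.

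A reader might infer more than the documents support:

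- *That relapse goes unreported to Week 26 in all 30% to 40% who stop.* All AEs are collected to Follow-up 2, late stoppers have no gap, and serious related relapses stay reportable. The section sets a minimum and still requires all AEs to be kept in the patient files.
- *That the planned relapse count is biased.* The treatment-emergent count loses nothing from this gap.
- *That the SAP reports relapse nowhere else.* It plans a follow-up-period AE table, and parts of the SAP are redacted.
- *That the statement about stopping drug cannot be tested.* Relapse is fully collected for 28 days after the early end-of-treatment visit, so it can be tested in part.
- *That early stoppers are at highest risk.* The documents do not show this.

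HCRU records hospital, home-hospital and emergency visits, which overlap closely with the relapse definition. That helps for patients who keep full visits. Under the reduced follow-up options in Table 6.2.5.1:1 it is not assured, because HCRU is described with the efficacy assessments. After baseline, PANSS is scheduled only at one mid-treatment visit and at end of treatment. Section 6.2.5.2 also refers to the investigator site file, which is not available here and might address the point.

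**Conclusion.** The point holds for patients who stop before about Weeks 20 to 22. Between Follow-up 2 and Week 26, a relapse that is non-serious or judged unrelated is not a required AE report. That does not fit the unlimited duty in Section 5.2.5, and it leaves the relapse endpoint with unequal follow-up.

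About 10% to 13% of planned patient-time is uncovered, given uniform stopping and a 35-day lag. For that scenario it is an upper bound, because consent withdrawal ends contact (Section 3.3.4.3) and that time cannot be recovered under any rule. Front-loaded stopping would raise the figure and late stopping would lower it. If the hazard doubled after stopping, about 17% to 22% of relapses would fall in the gap.

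The consequence is confined to the follow-up-period AE table and to any relapse incidence to Week 26. The endpoint is descriptive, and no sample size, alpha or power figure changes. The change is worth making because it is cheap.

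**What to change.** 1. **Protocol 5.2.6.2.1.** Reconcile with Section 5.2.5 by adding *schizophrenia relapse (as defined in Section 5.2.5)* to the events reported whatever their cause from Follow-up 2 to Week 26.
2. **SAP 7.8.1.** State the observation window for incidence of relapse. Add one descriptive table of patients with relapse from first dose to Day 183 in the treated set, regardless of treatment status, beside the treatment-emergent count.
3. **Patients already past that period.** Give a supplementary listing from HCRU entries for hospitalisation, home hospitalisation and emergency visits due to psychotic symptoms. State that it is incomplete.

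The cost is one bullet, a few more AE entries at visits that are already scheduled, and one table with a listing.
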